Contact information for telephone interviews will be accessible only to specified interviewing personal via a password protected mechanism. Collected telephone interview data will be stored in separate tables using the unique study identifier, as the primary key. These data will not be tied to the PHI collected as part of the contact information. All interview data will be stored on a password protected server and adhere to DCRI electronic safeguards.

Statistical Considerations

PROSPER will apply statistical protocols with pre-specified inclusion/exclusion criteria, analytic plans and sensitivity analyses. The analytic framework for PROSPER will, in general, utilize a “causal inference method”, or propensity scoring methods, to compare the safety and effectiveness of two or more stroke prevention, treatment, and management strategies. Standardized difference will be used to assess the balance across compared groups with respect to potential confounding variables in propensity score analysis.

Our primary end point, “home time”, will be analyzed using a linear regression model with transformations as necessary. Time to event outcomes (e.g. time-to-death, time to readmission) will be analyzed using the Cox proportional hazard model. Based on the models, the Wald’s tests will be used to test the significance of the treatment effects. After fitting models, the marginal residuals from the model will be used to test the goodness-of-fit of the proportional hazards model, with special attention to the proportionality assumption. When this assumption is not supported by the data, possible treatment and time interactions and other possible time-dependent covariates will be used to account for this non-proportionality. The resulting p-values that are less than 5% will be considered evidence of significant marginal differences across the cohorts.

Dichotomous outcomes (e.g. mRS, death, readmission) and continuous outcomes (e.g. Barthel Index, home time as a continuous measure) will be analyzed using multivariate logistic regression and multivariable linear regression models. We will perform subgroup analyses and/or advanced statistical modeling to determine the possible interaction between the treatment and patient characteristics and estimate the heterogeneity of treatment effects to reflect the individualization of results from the analyses. Our analyses will also account for clustering of patients within hospitals using generalized estimating equations (GEE).

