**Study Population *N Patients* *N Sites* % Remained**

1. Starting Population: All PROSPER (GWTG-Stroke linked to CMS\*) patients enrolled in a fully-participating GWTG hospital with a final clinical diagnosis of acute ischemic stroke in year 2014 104,423 1,436
2. Exclusions:
 

1) Patients FFS ineligible	-5,582	-2	94.7%
2) Patients discharged before April 2014	-23,467	-15	76.3%
3) Patients left AMA/discharge disposition UTD/missing	-255	-0	99.7%
4) Patients transferred out	-1,486	-4	98.0%
5) In-hospital deaths	-4,148	-2	94.4%
6) Discharge AD not documented (historic and new)	-31,801	-383	54.2%
7) Patients with AD contraindications	-8,507	-7	77.4%
	=29,177	=1,023	
3. Final Study Population: 29,177 patients from 1,023 hospitals  
Study period: Apr 1, 2014 – Dec 31, 2014

\* Linkage to CMS implies that patients are at age of 65 or older, linked with first admission

**Table.** New AD variable by historic AD variable check in the IS study population.

Antidepressant Medication(s) At Discharge (New)	Antidepressant Medication(s) At Discharge (Historic)			
	Missing	1= Yes	2 = No/ND	Total
. = Missing	0 0 0 0	6075 20.82 27.23 99.72	16234 55.64 72.77 99.71	22309 76.46
1 = Yes, SSRI	1063 3.64 99.16 15.63	9 0.03 0.84 0.15	0 0 0 0	1072 3.67

Antidepressant Medication(s) At Discharge (New)	Antidepressant Medication(s) At Discharge (Historic)			
	Missing	1= Yes	2 = No/ND	Total
2 = Yes, any other antidepressant class	438 1.50 98.21 6.44	8 0.03 1.79 0.13	0 0 0 0	446 1.53
3 = No/ND	5302 18.17 99.10 77.94	0 0 0 0	48 0.16 0.90 0.29	5350 18.34
Total	6803 23.32	6092 20.88	16282 55.80	29177 100

Color code: AD Yes patients, AD No patients

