Hospital characteristics				
Teaching status				
Rural location				
Region				
Primary Stroke Centers				
Comprehensive Stroke Centers				
Hospital size, mean (SD)				
Annual IS admission volume, mean (SD)				

All numbers presented are proportions of patient in the study population, unless specified otherwise.

\* P-values from chi-squared tests for independence for categorical variables and Wilcoxon rank sum tests for continuous variables

## 2. Objective 2

**Aim:** To estimate the associations between antidepressant use (any vs. none) and outcomes (home time, all-cause mortality, all-cause readmission recurrent stroke [ischemic, hemorrhagic], cardiovascular rehospitalization, and depression-related hospitalization [suicidality or major depressive episode] following discharge).

**Analysis:** Because patients who receive AD may differ from those who do not on important baseline and clinical characteristics that may affect the likelihood of adverse events, we will use inverse probability of treatment weighting (IPW) when assessing treatment effects. IPT weighting will be accomplished in two steps: First, we will use a logistic regression model to assign a probability of treatment selection to each patient based on the distribution of a defined set of covariates (listed above). The binary outcome for the selection model will be AD treatment (Y/N). In the second step, we will weight subject by the inverse of this assigned treatment probability, resulting in a pseudo-randomization of patients to AD vs. no AD treatment. The distribution of baseline patient characteristics for each treatment group will be assessed after weighting to determine adequacy of the selection model.

Following IPW, we will compare primary and secondary endpoints between treatment groups. Unadjusted rates of all-cause mortality, all-cause readmission, CV readmission, depression-related admission and stroke/TIA readmission will be examined using a Cox proportional hazards model with AD use as the single independent variable. Adjusted event rates will then be estimated using the same model with IPW included for each subject. Within-hospital clustering will be accounted for using robust estimator approach.

Home time will be examined first as a continuous variable in a linear regression model and then as a dichotomous outcome in an IPW-weighted logistic regression model, using 100% of time spent at home over 1 year as the primary outcome of interest.

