Methods will be repeated for SSRI vs. non-SSRI with corresponding modeling of clinical outcomes.

**Output:** [Table 2](#) (AD vs No AD), [Table 3](#) (SSRI vs not SSRI)

**Table 2.** AD use and clinical outcomes following ischemic stroke discharge.

Outcomes	AD	No AD (ref)	Unadjusted HR (95% CI)	Adjusted HR (95% CI)	P-value
----------	----	----------------	---------------------------	-------------------------	---------

**Table 3.** SSRI vs. non-SSRI use and clinical outcomes following ischemic stroke discharge.

Outcomes	SSRI	Other AD (ref)	Unadjusted HR (95% CI)	Adjusted HR (95% CI)	P-value
Home time: 100% (OR)					
All-cause mortality					
Readmission					
All-cause					
Cardiovascular					
Stroke/TIA					
Ischemic Stroke					
Hemorrhagic Stroke					
Depression-related readmission					
			Unadjusted Difference (95% CI)	Adjusted Difference (95% CI)	
Home time days, mean (SD)					

[figure not shown]
### 3. Objective 3

**Aim:** To describe 1y mortality and readmission outcomes by plotting the cumulative incidence functions.

**Analysis:** We will limit the population to patients naïve to AD on admission and construct Kaplan-Meier curves for all-cause mortality at 1 year following the index hospitalization for patients prescribed AD at hospital discharge. Log-rank tests will be used to examine mortality differences between AD treatment groups.

For the other non-mortality endpoints, we will calculate incidence at 1 year based on estimates from the cumulative incidence function, to account for the competing risk of mortality. Gray tests will be used to test for differences between groups for these outcomes.

We will then restrict the study population to patients receiving AD at hospital discharge and analyses will be repeated for SSRI vs. non-SSRI antidepressants.

**Figure X.** Cumulative incidence plots for mortality and readmissions by AD types (Yes vs No, and again for SSRI vs Non-SSRI).

### 4. Objective 4

**Aim:** Perform subgroup analyses.

**Analysis:** Because AD use and outcomes may vary by patient characteristics, we will repeat modeling of these associations by the following subgroups: Age (65-80, 80-90, 90+), sex (male vs. female), race (white vs. non-white), NIH stroke scale (<16 vs. ≥16), and medical history of depression.

Repeat Tables 2 and 3 in subgroups defined.

### 5. Objective 5

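### Objective 3's log-rank and Gray tests make no stated allowance for hospital clustering, so their p-values may be misstated, in either direction and probably by little

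*SAP*

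**What the plan says.** The Protocol, under Statistical Considerations, states: "Our analyses will also account for clustering of patients within hospitals using generalized estimating equations (GEE"). The same section treats p-values below 5% as evidence of a difference.

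The SAP applies the clustering rule under III. Analysis Tasks, 2. Objective 2, after the Cox models: "Within-hospital clustering will be accounted for using robust estimator approach".

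Under 3. Objective 3 the aim is "To describe 1y mortality and readmission outcomes by plotting the cumulative incidence functions". The analysis text begins "We will limit the population to patients naïve to AD on admission" and then names two tests. For mortality, "Log-rank tests will be used to examine mortality differences between AD treatment groups". For the endpoints with death as a competing risk, "Gray tests will be used to test for differences between groups for these outcomes". The comparison is then repeated for SSRI versus non-SSRI. No stratification, robust variance or other allowance for hospital is stated for either test, and nothing says that the Objective 2 sentence carries over.

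**The concern.** Patients from one hospital may share case mix, care and discharge practice, so their outcomes may be correlated. The usual variance of the log-rank and Gray statistics ignores this. The SAP would then report p-values for mortality and readmission on two variance assumptions, robust in Objective 2 and independent in Objective 3, without saying so.

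Objective 2 does not make the Objective 3 p-values redundant. It uses all patients, and among AD users with known prior status 5,678 of 7,514 (75.57%) were already on an AD at admission. Objective 3 is the only stated outcome comparison confined to AD-naive patients, and prior AD use is not among the Objective 4 subgroups. At stake is whether the nominal 5% level of these tests can be trusted.

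**Working it through.** **1. The plan's own count.** From the SAP Study Population table:

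- Patients: 104,423 − 5,582 − 23,467 − 255 − 1,486 − 4,148 − 31,801 − 8,507 = 29,177.
- Hospitals: 1,436 − 2 − 15 − 0 − 4 − 2 − 383 − 7 = 1,023.

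Both agree with "Final Study Population: 29,177 patients from 1,023 hospitals".

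**2. The Objective 3 comparison.** From the tables under SAP II. Variables, 1. Primary exposure variable:

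- AD-naive with AD at discharge: 1,836. AD-naive without: 20,601. Total 22,437, of whom 8.2% are treated.
- Mean per hospital: 22,437 / 1,023 = 21.9. The number of hospitals in this subset is not given, so 1,023 is assumed. Fewer hospitals would make the mean larger.
- AD-naive on SSRI: 262. On other AD: 118. Total 380.

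**3. Formula.** For a patient-level exposure, the ratio of true to assumed variance is about D = 1 + (m − 1) × ρx × ρy. Here ρx is the intraclass correlation (ICC) of exposure, ρy that of outcome, and m the size-weighted mean number of patients per hospital. The true error of a nominal 5% two-sided test is 2[1 − Φ(1.96/√D)].

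The documents give neither ICC, nor the spread of hospital sizes. Assumed: m = 21.9 (equal hospitals) or 21.9 × (1 + 1²) = 43.9 (coefficient of variation of size 1), and the ICCs in the table. If every hospital has the same AD share, ρx = −1/(m − 1) and D = 1 − ρy.

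| ρx | ρy | m | D | True error |
|---|---|---|---|---|
| same share everywhere | 0.01–0.05 | either | 0.99–0.95 | 4.9–4.4% |
| 0.05 | 0.02 | 21.9 | 1.021 | 5.2% |
| 0.10 | 0.02 | 43.9 | 1.086 | 6.0% |
| 0.10 | 0.05 | 43.9 | 1.214 | 7.5% |
| 0.20 | 0.05 | 43.9 | 1.429 | 10.1% |

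Third row: D = 1 + 42.9 × 0.10 × 0.02 = 1.086, 1.96/√1.086 = 1.88, two-sided tail 6.0%.

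If exposure were fixed by hospital (ρx = 1), D would be 1.21 to 3.14 and the error 7.5% to 27%. That does not apply here, because AD is prescribed patient by patient.

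**4. Simulation of the ordinary log-rank test with no treatment effect.** Inputs: 22,437 patients, 1,023 hospitals, 8.2% treated, and 1-year mortality of 22% (assumed, within the 15–30% in the Protocol Introduction). Hospital frailty is log-normal and hospital prescribing logit-normal. There were 1,500 to 2,000 runs per cell, with a Monte Carlo standard error of 0.5 to 0.6 percentage points.

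| Prescribing across hospitals | Frailty SD | Equal hospitals | Size CV 1 |
|---|---|---|---|
| same share | 0.5 | 4.0% | 4.9% |
| same probability | 0.2; 0.5 | 5.3%; 5.5% | 4.5%; 5.2% |
| logit SD 0.5 | 0.2; 0.5 | 4.9%; 4.8% | 4.9%; 5.1% |
| logit SD 1.0 | 0.2; 0.5 | 5.1%; 6.6% | 5.2%; 8.4% |

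The logit SDs are not on the scale of ρx, so the two tables should not be matched row by row. They agree in pattern: only strong variation in both prescribing and outcome moves the error clearly above 5%.

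**5. SSRI versus other AD.** With 380 AD-naive patients, or 1,518 if the naive restriction is not kept (the SAP is unclear), there are 0.4 to 1.5 patients per hospital if spread over 1,023. Simulated error, with frailty SD 0.5, logit SD 0.5 or 1.0, size CV 1 and 4,000 runs, was 4.7% to 5.4%.

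The Gray test was not simulated. The formula is taken to apply to it in the same way.

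**The case against.** Three arguments can be made for leaving the text alone.

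- **Objective 3 is descriptive.** Its aim is to describe and its output is a figure, while treatment effects are estimated in Objective 2. This lowers the stakes, but the text still specifies two hypothesis tests between treatment groups and does not call them descriptive.
- **The Protocol sentence is a rule for regression models.** It closes a paragraph on logistic and linear regression and subgroup modelling. If it governed every p-value, the baseline tests in Objective 1 would also breach it. This reading is fair. The wording nevertheless carries no exception, and Objective 3 compares outcomes by treatment, which the baseline tests do not.
- **Clustering is not the main weakness.** The Objective 3 tests are also unadjusted for confounding. That is true but separate: it concerns bias, and this point concerns variance.

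A reader might also go further and infer that the p-values are certainly too small. The documents do not support that. Treated and untreated patients can come from the same hospital, so the sign depends on two ICCs that are not reported, and the error can fall below 5%. Nor does the loss of 383 of 1,413 hospitals (27%) under "Discharge AD not documented (historic and new") settle the matter. It shows that documentation of the field clusters by hospital. Those hospitals leave the analysis, and their loss says nothing about how prescribing varies among the 1,023 that stay.

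**Conclusion.** The gap is real and minor. Objective 3 names tests that assume independent patients, beside a Protocol statement and an Objective 2 method that do not. The p-values may be slightly too large if prescribing shares are similar across hospitals, and too small if prescribing and outcomes both vary by hospital.

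For AD versus no AD, the true error of a nominal 5% log-rank test is about 4% to 10% over the assumed range, and near 5–6% in middle cases. For SSRI versus other AD it stays close to 5%. These figures rest on assumed ICCs, hospital-size spread, 22% mortality, a two-sided test and 1,023 hospitals in the AD-naive subset. The documents settle neither direction nor size, which is a reason to use a method that is valid either way.

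**What to change.** Keep the Kaplan-Meier and cumulative incidence curves in Objective 3 and replace the two test sentences:

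- Mortality: take the p-value from a Cox model with AD group as covariate and hospital-clustered robust variance.
- Other endpoints: take the p-value from a Fine-Gray model with hospital-clustered robust variance.
- SSRI versus other AD: use the same code for consistency, although little change is expected, and state whether the AD-naive restriction applies.

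Alternatively, label the Objective 3 curves descriptive, drop the tests, and take inference from Objective 2. This is simpler, but leaves no test confined to AD-naive patients.

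The cost is about two sentences in the SAP and a standard software option. The p-values will change slightly and may be a little larger. Neither option deals with confounding in Objective 3.

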CONFIDENTIAL

The information contained in this proposal is confidential and the property of Duke University. It is intended solely for the use of the recipient in evaluating whether or not to enter into a participation agreement with Duke University or for site personnel training, and not for any other purpose. This information is not to be distributed outside the recipient organization.

PROSPER

(Patient-centered Research into Outcomes Stroke patients Prefer and Effectiveness Research)

Retrospective Power Analysis:

Based on our other work and the overall anticipated sample size of 450,000 ischemic stroke records in the GWTG-Stroke between 2007 and 2012 to maintain >90% power for the majority of subgroup analyses

Prospective Power Analysis:

The prospective study population comprises 5,000 patients in the combined AVAIL and PROSPER call center datasets. Based on estimated sample sizes, we will have greater than 90% power to detect patient-reported outcome differences of 7% (oral anticoagulant analysis), 6% (statin analysis), and 8% (anti-depressant analysis) between treated and untreated groups.

Governance

Science and Publications Committee

The Publications Committee of PROSPER will include the investigative team as well as clinical and academic representatives from participating sites. The Publication Committee will function as an independent body of scientific and medical experts with the following charter:

- a. The Publication Committee shall be responsible for the review and approval of analyses suggested by both internal and external investigators;
- b. The Publication Committee shall read and constructively critique all abstracts and manuscripts prior to submission for presentation or publication;
- c. The Publication Committee shall consider each manuscript proposal with due regard for the scientific merit of the proposed publication with the aim of promoting the dissemination of scientific and medical knowledge;
- d. Decisions of the Publication Committee shall be by majority vote, and there shall be no restrictions on the topics or analytical approaches used in developing manuscripts and presentations, other than those imposed by the Publications Committee;
- e. All manuscripts approved by the Publication Committee shall conform to the Uniform Requirements for Manuscript Submitted to Biomedical Journals, including, but not limited to the standards for authorship.

Executive Committee

TBD

Steering Committee

TBD

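### SAP Objective 4 estimates associations within subgroups but plans no contrast between them, so the interaction analysis mentioned in the Protocol has no method

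*SAP*

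**What the plan says.** SAP III. Analysis Tasks, Objective 4, reasons that antidepressant (AD) use and outcomes might differ between kinds of patient. The method is "we will repeat modeling of these associations by the following subgroups", namely "Age (65-80, 80-90, 90+), sex (male vs. female), race (white vs. non-white), NIH stroke scale (<16 vs. ≥16), and medical history of depression". The output instruction is "Repeat Tables 2 and 3 in subgroups defined". Table 3 has, for each outcome row, group values, an unadjusted and an adjusted estimate with 95% CI, and one p-value for the treatment comparison. Table 2 has the same columns. Nowhere does the SAP name a treatment-by-factor term, a heterogeneity test or an interaction p-value.

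The Protocol, under Statistical Considerations, states: "We will perform subgroup analyses and/or advanced statistical modeling to determine the possible interaction between the treatment and patient characteristics". In the same sentence it undertakes to "estimate the heterogeneity of treatment effects to reflect the individualization of results from the analyses". It gives no model term, scale or test for this. On significance in general it says: "The resulting p-values that are less than 5% will be considered evidence of significant marginal differences across the cohorts". Under Retrospective Power Analysis it relies on 450,000 anticipated records "to maintain >90% power for the majority of subgroup analyses".

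**The concern.** A stratum-specific estimate describes the association in that stratum. Whether it differs from the association in another stratum is a separate question, and it needs a contrast with its own standard error. When strata carry very different amounts of information, one common effect will often reach significance in the larger stratum and miss it in the smaller.

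History of depression is an obvious candidate modifier in an antidepressant study, and its strata are very unequal. A uniform benefit or harm could look as if it were confined to patients without prior depression. Such a pattern has consequences here, because Aim 3 of the Protocol turns the comparative results into decision aids for individual patients.

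**Working it through.** **1. Inputs.** SAP II. Variables, Primary exposure variable, gives these counts by history of depression:

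| Comparison | With history | Without history |
|---|---|---|
| AD yes / no | 3,309 / 1,032 | 4,284 / 20,552 |
| SSRI / other AD | 474 / 193 | 598 / 253 |

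They agree with the SAP's totals: 3,309 + 1,032 = 4,341; 4,284 + 20,552 = 24,836; 4,341 + 24,836 = 29,177; and 1,072 + 446 = 1,518 for the SSRI comparison. No stratum sizes are given for the other four factors.

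**2. The plan's own power figure.** The subgroup power above 90% cannot be reproduced, because no effect size, SD, event rate or stratum size is given. It was based on 450,000 records against 29,177 analysed. Other things equal, standard errors are √(450,000/29,177) = 3.9 times larger than on that basis.

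**3. Information per stratum**, n₁n₂/(n₁+n₂), for AD versus none:
- With history: 3,309 × 1,032 / 4,341 = 786.7
- Without history: 4,284 × 20,552 / 24,836 = 3,545.0
- Ratio of standard errors: √(3,545.0/786.7) = 2.12

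**4. Power in each stratum under one common effect.** Assume two-sided 5% and 90% pooled power, so the pooled expected z is 1.960 + 1.282 = 3.242. Each stratum's expected z is this times √(its information / 4,331.7).
- With history: 3.242 × 0.426 = 1.38, power 0.282
- Without history: 3.242 × 0.905 = 2.93, power 0.835

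**5. Chance that exactly one stratum is significant**, pA(1−pB) + pB(1−pA):
- 0.282 × 0.165 + 0.835 × 0.718 = 0.646, about 65%
- Of this, 60 percentage points are the pattern significant without history, not significant with history.

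**6. Range over the assumed pooled power:**

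| Pooled power | AD vs none | SSRI vs other AD |
|---|---|---|
| 50% | 45% | 41% |
| 80% | 62% | 51% |
| 90% | 65% | 47% |
| 95% | 63% | 41% |
| 99% | 55% | 26% |

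With no effect at all, the figure is 2 × 0.05 × 0.95 = 9.5%. A valid interaction test at 5% would signal false heterogeneity in 5% of studies in every row.

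**7. What an interaction test could detect** at 90% power, 3.242 × √(1/I₁ + 1/I₂), on a standardized scale:
- AD versus none: 3.242 × √(1/786.7 + 1/3,545.0) = 0.128 SD
- SSRI versus other AD: information is 474 × 193 / 667 = 137.2 and 598 × 253 / 851 = 177.8, giving 3.242 × √(1/137.2 + 1/177.8) = 0.368 SD

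**8. Volume.** Age has three strata and the other four factors two each (yes/no assumed for depression history), so 11 strata. With Table 3's nine outcome rows, assumed for Table 2 as well, and two comparisons, there are 11 × 9 × 2 = 198 adjusted estimates. About 198 × 0.05 = 9.9 would be significant if every null held. One interaction test per factor gives 5 × 9 × 2 = 90 tests, with 4.5 expected false positives.

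**The case against.** A reader might infer that the SAP judges subgroups by which strata are significant. Neither document states such a rule. Tables 2 and 3 also show adjusted estimates with 95% CIs, so disjoint strata can be compared approximately from the planned output. The Protocol's 5% criterion concerns differences between the compared cohorts, not between strata. The misreading is therefore a risk that the plan leaves open and does not itself commit.

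A reader might also infer that the SAP replaces or contradicts the Protocol. It does not. The Protocol names subgroup analyses as one permitted route to its aim, so stratified models alone satisfy its wording. Objective 4 as titled only examines associations within subgroups, and stratified estimates meet that. What stands is that the heterogeneity aim is stated in one document and specified in neither.

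On size, if every stratum did have at least 90% power, as the Protocol hopes for most subgroups, discordance between two strata would be at most 2 × 0.9 × 0.1 = 18%. That power claim rests on a much larger cohort and an unstated effect, so it cannot be carried over.

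Two further points are fair. Interaction tests do not remove multiplicity, and 22 of the 198 estimates concern the depression-related outcome that the SAP already calls exploratory. In the SSRI comparison, with 1,518 patients, an interaction test would miss moderate heterogeneity. Both points affect how the results are labelled and do not remove the need for a between-stratum estimate.

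**Conclusion.** The point holds as a gap in specification: the SAP does not carry out the heterogeneity analysis that the Protocol mentions, although it could do so with data already held. The calculation shows that apparent disagreement between the depression-history strata is a likely result even when the effect is the same in both.

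The percentages are indicative. They assume a two-sided 5% level, independent strata, a normal approximation, and no variance inflation from weighting or hospital clustering. The pooled power is assumed and is not stated in the documents. The remaining factors cannot be sized from the documents. This is worth correcting before the subgroup results are produced. It does not affect the main comparisons.

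**What to change.** Add to SAP Objective 4:

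- **Model.** For each of the five factors, fit the inverse-probability-weighted model in the full cohort for that comparison, with the factor main effect and treatment × factor, keeping the hospital-robust variance. The planned Cox model contains treatment alone, so main effects must be added too. There are six interaction coefficients in all, with a 2-df test for three-level age.
- **Report.** Beside the stratum estimates, give the ratio of hazard ratios (the ratio of odds ratios for 100% home-time, the difference in differences for home-time days) with 95% CI and interaction p-value.
- **Interpretation.** State that a claim of differing effect rests on the interaction estimate and its CI, not on which strata are significant. State that a non-significant interaction is not evidence of a uniform effect, especially for SSRI versus other AD. Label the roughly 90 interaction tests as exploratory.
- **Balance.** Check weighted covariate balance within each stratum. Objective 2 specifies the check by treatment group only.

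The cost is modest extra modelling for each outcome and both comparisons. The interaction estimates will be imprecise in the SSRI comparison, and fewer subgroup claims will be possible.

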## II. Variables

## 1. Primary exposure variable

Any antidepressant prescription at hospital discharge (yes vs. no, derived from a combination of historic and revised antidepressant variables)

- Historic AD variable: AD Yes / AD No
- New AD variable: Yes, SSRI / Yes, other AD class

SSRI (selective serotonin reuptake inhibitors) are defined as any of the following: Citalopram (Celexa), Escitalopram (Lexapro), Fluoxetine (Prozac), Paroxetine (Paxil, Pexeva), Sertraline (Zoloft). Other antidepressant therapy will be defined as all other non-SSRI antidepressants. SSRI analyses will be limited to patients with complete data on the new AD variable.

AD	Frequency	Percent	SSRI	Frequency	Percent
Yes	7,593	26.02	Yes, SSRI	1,072	70.62
No	21,584	73.98	Yes, other AD	446	29.38
Total	29,177	100	Total	1,518	100

Variable	Level	Overall (N=29177)	AD YES (N=7593)	AD NO (N=21584)	P-value+
History of depression	Yes	4341 14.88	3309 43.58	1032 4.78	<.0001
	No	24836 85.12	4284 56.42	20552 95.22	
AD prior to admission	Yes	6432 22.28	5678 75.57	754 3.53	<.0001
	No	22437 77.72	1836 24.43	20601 96.47	
	Missing	308 1.06	79 1.04	229 1.06	

Variable	Level	Overall (N=1518)	SSRI YES (N=1072)	SSRI NO (N=446)	P-value+
History of depression	Yes	667 43.94	474 44.22	193 43.27	0.7361
	No	851 56.06	598 55.78	253 56.73	
AD prior to admission	Yes	1125 74.75	800 75.33	325 73.36	0.4238
	No	380 25.25	262 24.67	118 26.64	
	Missing	13 0.86	10 0.93	3 0.67	

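### The Cox Wald test with a robust variance gives p < 0.0001 whenever one arm has no events, so sparse cells of Table 3, mainly hemorrhagic stroke in subgroups, can show false SSRI differences

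*SAP*

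**What the plan says.** The analysis is assembled from both documents.

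- **Model** (SAP, III. Analysis Tasks, Objective 2). Mortality and readmission outcomes "will be examined using a Cox proportional hazards model with AD use as the single independent variable". For the adjusted analysis, "Adjusted event rates will then be estimated using the same model with IPW included for each subject".
- **Variance** (same place). "Within-hospital clustering will be accounted for using robust estimator approach".
- **Test and threshold** (Protocol, Statistical Considerations). "Based on the models, the Wald’s tests will be used to test the significance of the treatment effects". Then: "The resulting p-values that are less than 5% will be considered evidence of significant marginal differences across the cohorts". The SAP does not name the test behind the P-value column of Table 3.
- **SSRI comparison** (SAP, Objective 2). The same methods are repeated for SSRI vs other antidepressants and reported in Table 3, which has separate rows for hemorrhagic stroke and depression-related readmission.
- **SSRI population** (SAP, Primary exposure variable). "SSRI analyses will be limited to patients with complete data on the new AD variable". That leaves 1,072 SSRI and 446 other-antidepressant patients.
- **Subgroups** (SAP, Objective 4). "Repeat Tables 2 and 3 in subgroups defined". The list gives 11 strata: three by age and two each by sex, race, NIHSS and history of depression.

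Neither document sets a minimum event count, a rule for an arm without events, or a penalised or exact alternative for Table 3.

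**The concern.** A rare outcome in a few hundred patients, split about 70:30, will sometimes have all its events in one arm. With a model-based variance this is harmless to the Wald test: the standard error diverges with the estimate and the test does not reject. The robust variance does not diverge, so the Wald ratio becomes enormous. A single event against none then passes the 5% rule by a wide margin.

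In such cells the result depends on which arm happens to be empty. The smaller other-antidepressant arm is empty more often, so most false results would show a higher hazard with SSRIs. In the hemorrhagic stroke row that would be read as a safety signal. Protocol Aim 3 intends the comparative results to feed patient decision aids.

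**Working it through.** **1. Counts in the SAP.** 1,072 + 446 = 1,518, the stated total. With a history of depression: 474 SSRI and 193 other. Without: 598 and 253. Check: 474 + 598 = 1,072 and 193 + 253 = 446. Only these strata have stated sizes. The documents give no event rates, so risks are assumed, equal in both arms (true HR = 1).

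**2. Why the robust Wald test fails.** Let all D events fall in the SSRI arm, let b be the log HR, and let r be the ratio of other-antidepressant to SSRI patients at risk. As b grows:

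- Each event contributes about r·e^(−b) to the information, so I ≈ D·r·e^(−b). The model-based SE, 1/√I, grows without bound.
- Each event's score residual is also about r·e^(−b), and the other residuals are negligible when D is small. With events in different hospitals, the robust variance is D·(r·e^(−b))² / (D·r·e^(−b))² = 1/D.
- The robust SE is therefore about 1/√D. If all D events fell in one hospital it would be about 1, which is still finite.

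**3. Worked case: 3 events in 474 vs 0 in 193.** Iteration stops at log HR 15.6, with model SE 2,162 and robust SE 0.581 (1/√3 = 0.577).

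- Model-based Wald: z = 15.6/2,162 = 0.007.
- Robust Wald: z = 15.6/0.581 = 26.9.
- Log-rank: expected SSRI events 3 × 474/667 = 2.13; variance 3 × 0.711 × 0.289 = 0.617; z = (3 − 2.13)/√0.617 = 1.11.

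The same holds with weighting. In 3,000 random data sets with one empty arm (1 to 8 events in the other arm, weighted or not, 40 to 300 hospitals, two stopping rules), all 3,000 gave p < 0.05. The largest p was about 2 × 10^(−56).

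**4. How often exactly one arm is empty.** For observed risk p and arm sizes n1, n0:

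P = (1−p)^n0 · [1 − (1−p)^n1] + (1−p)^n1 · [1 − (1−p)^n0]

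History of depression, p = 0.5%: 0.995^193 = 0.380 and 0.995^474 = 0.093, so P = 0.380 × 0.907 + 0.093 × 0.620 = 0.345 + 0.058 = 0.40. The other-antidepressant arm is the empty one in 0.345/0.402 = 86% of these cases.

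| Population | 0.25% | 0.5% | 1% | 2% |
|---|---|---|---|---|
| Table 3 undivided (1,072 vs 446) | 35% | 11% | 1.1% | 0.0% |
| Depression history yes (474 vs 193) | 55% | 40% | 15% | 2% |
| Depression history no (598 vs 253) | 52% | 30% | 8% | 0.6% |

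**5. False-positive rate of the robust Wald test.** Simulated with HR = 1 and 20% one-year mortality (assumed):

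| Population | 0.3% | 0.5% | 1% | 2% |
|---|---|---|---|---|
| Depression history yes | 54% | about 45% | 19% | 6% |
| Table 3 undivided | about 35% | about 17% | 4–5% | 3–5% |

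These partly exceed step 4 because deaths remove some events. If deaths are spread evenly over the year, average follow-up is about 0.9 year, and 0.5% × 0.9 = 0.45% gives P = 0.44 in the depression-yes stratum. Where the risk is taken as already observed, the simulated rates at 0.5% are 42% and 14%.

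**6. Where the excess comes from.** In those latter simulations of the depression-yes stratum, total rejection was 41.9%, 17.6% and 6.2% at 0.5%, 1% and 2% risk, of which 41.2, 15.9 and 1.9 points came from empty arms. The remainder is 0.7, 1.7 and 4.3 points, so cells with events in both arms are not inflated.

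**The case against.** **Certainty.** A reader might infer that Table 3 as a whole will report false SSRI differences. The documents do not support that. They give no event rates, and at 1% risk or more the undivided table holds its 5% level. Sizes of strata other than history of depression are not given either.

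**The depression-related row.** A reader might also count this row as rare. Its definition, unlike that for stroke/TIA readmission, is not limited to the principal diagnosis. It includes codes for major depression, and 43.94% of the SSRI analysis set has a history of depression. It could be common, in which case empty arms are unlikely. The SAP also labels it exploratory. It counts only if it proves rare.

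**The rule is a composite.** The Wald test and the 5% level come from the Protocol's general framework for three treatment areas. That framework names GEE for clustering, whereas the SAP names a robust estimator. This is fair, but the SAP offers no other test for Table 3, and the combination is the natural reading.

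**Other output.** Objective 3 plans cumulative incidence curves and Gray tests, which do not use the diverged estimate. They do not supply Table 3's p-value, do not cover the subgroups, and appear to be limited to patients not on antidepressants at admission. An analyst would probably notice an absurd hazard ratio beside a zero count, but the plan does not say what to do then, which leaves a choice made after seeing the data.

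**Not every empty arm is a false signal.** In 1,072 vs 446, about 11 SSRI events against none, or 3 other-antidepressant events against none, would be significant by an exact test as well.

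**Conclusion.** The point stands for cells in which exactly one arm has no events. There the stated rule returns p < 0.0001 regardless of the evidence. The cell most exposed is hemorrhagic stroke in the subgroup repeats of Table 3. The undivided table is materially exposed only below about 1% one-year risk.

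The mechanism needs no assumption about rates. The size does: it rests on assumed, equal one-year risks of 0.3% to 2% and, for the main simulation, 20% mortality. In the depression-yes stratum, whose size the SAP states, the false-positive rate runs from about 54% down to 6% over that range. The primary home-time outcome is untouched. This is a gap in secondary and exploratory results that should be closed before analysis, and it does not undermine the main comparison.

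**What to change.** Add to SAP Objectives 2 and 4:

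> *If either arm has no events for an outcome in a table or stratum, no HR, robust Wald CI or p-value is given; event counts and cumulative incidence by arm are shown, and the 5% rule is not applied.*

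If a p-value is still wanted in such a cell, label it supplementary and take it from a test that does not use the diverged estimate: an unweighted exact test, or a model-based log-rank (score) test. In the simulations with 20% mortality, the ordinary log-rank test rejected in 0.5–5.5%. Note beside it that it reflects neither the IPW weighting nor the hospital clustering. A robust score test is not a clean substitute: its false-positive rate was 7.3% in the depression-yes stratum at 0.5% risk, and it gave p = 0.03 for 5 events vs 0 in 1,072 vs 446.

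The cost is one sentence, and some sparse cells will show counts in place of a hazard ratio. No usable estimate is lost, because the ratio cannot be estimated there.
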